D5. Data Analysis. Data will be managed using REDCap (Research Electronic Data Capture; which is HIPAA compliant).⁶⁸ Primary analysis will be group differences in TUG times (primary outcome) at the 12-week time point. As a pilot feasibility study, data will only be analyzed for participants with sufficient intervention exposure, defined as six weeks. For participants who withdraw at or beyond six weeks of intervention, an early termination test will be performed and carried forward as the end-point. Participants who withdraw before completing six weeks will be lost to follow-up and no imputation will be performed for missing data. Attempts will be made to test all participants at 24-weeks. However, missing 24-week data will not be imputed from the 12 week measurement, as this would bias the effect following the primary end-point (i.e., it is expected that both groups would have worse 24- compared to 12-week outcomes). Group differences will be based on a linear model with TUG as the outcome and explanatory variables being primary medical diagnosis (PAD, DM, or both), rehabilitation site, treatment group, and baseline TUG. Group differences will be determined by this single test to protect against Type I error (α level: 0.05).

Secondary analyses will include differences at 12-weeks in the other outcomes (2MW, 5mW, PEQ-MS 12/5, Houghton Scale, PSFS, Activity level, number of healthcare provider visits, and number of hospital encounters) using the same method as for the primary outcome. A mixed-effects model with time as a fixed covariate across baseline, 12-, and 24-weeks will be used to evaluate long-term outcomes (24-week) and make inferences regarding the effectiveness of the intervention up to 12-weeks after intervention is complete. As with the other analyses, evaluation of the time trajectory will be conditioned on stratification variables and baseline values of the outcome measure. Also the mixed-effects model will not include data from subjects who drop prior to 6 weeks.

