The exploratory aim of identifying predictors of physical activity and disability will be analyzed by regression analysis. First, variables will be grouped into demographic/anthropometric, activity/mobility, health behaviors, physical health, amputated-limb health, contralateral-limb health, and cognitive/affective health, and healthcare use factors. A hierarchical process will be used to screen variables within each group of factors to identify the best predictors within each group. Finally, the best predictor variables from each group will be entered into a regression model to determine models containing subsets of the variables that predict the outcome, based on R^2_{adj} . The most parsimonious model will be identified by comparing the 10 best models, using partial F-tests.

D6. Sample Size Estimate. Sample size was estimated using TUG means and variances at discharge from the ongoing pilot study. In addition, literature was used to estimate long-term (> 3 months post-amputation) TUG scores for the population.^{60-62,69,70} Using 12.4 (3.9) seconds mean (SD) TUG time at rehabilitation discharge from the first 14 participants in the pilot study and 19.3 seconds as the average of TUG time reported for patients several months to years after amputation, a group difference of approximately 6.0 seconds was expected in TUG times at the 12-week time-point (primary end-point). With this group difference and an estimated SD of 6.0 (effect size = 1.0), 17 participants per group would provide 80% power to identify differences. The assumption is the EXP group will maintain or improve TUG times after the 12-week intervention and the CTL group will decline toward levels reported in the literature. A 3.4 second change in TUG represents a minimal detectable change for patients with lower limb amputation.⁶⁹

The goal is to enroll 44 participants and graduate 17 participants per group (n=34) at the 12-week test point. Based on data from the four participating hospitals, 150 patients will complete rehabilitation and achieve functional ambulation following dysvascular transtibial amputation

over the next 3 years. Based on the pilot study (Section C2), 60% of these patients are expected to meet inclusion/exclusion criteria (n = 90) and 50% of those will agree to participate (n = 45). A 20% loss to follow-up at 12 weeks (n=34) is estimated, which is twice the observed rates of studies with 12-week end-points that the PI has been involved with for other patient populations.

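### D5 counts a TUG taken at withdrawal, from week 6 on, as the 12-week primary value; the SAP uses a different model, omits that test, and neither document says which governs

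*Protocol*

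**What the plan says.** Protocol D5 makes the group difference in TUG at 12 weeks the primary analysis, as one test at the 0.05 level. "Group differences will be based on a linear model with TUG as the outcome", with diagnosis, site, treatment group and baseline TUG as explanatory variables. Only participants with six weeks of intervention are analysed. For those who leave later: "For participants who withdraw at or beyond six weeks of intervention, an early termination test will be performed and carried forward as the end-point".

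For the later visit D5 takes the opposite line: "missing 24-week data will not be imputed from the 12 week measurement, as this would bias the effect following the primary end-point", the reason being that "it is expected that both groups would have worse 24- compared to 12-week outcomes". It adds: "Attempts will be made to test all participants at 24-weeks".

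D6 sizes the trial on a difference of about 6.0 s at week 12. It assumes that EXP holds or improves and that "the CTL group will decline toward levels reported in the literature".

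The SAP carries the same date as the protocol if its numeric date is read month first. It applies one maximum-likelihood repeated-measures model to all outcomes at 12 and 24 weeks, using all available data under missing at random. It says nothing about the early-termination test, carry-forward or the six-week rule, and does not name the one endpoint for which the trial is powered.

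**The concern.** There are two linked problems.

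First, the D5 rule labels a measurement taken up to six weeks early as a 12-week value. On D6's premise the arms are still separating during that time, so the early value generally understates the separation expected at week 12.

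Second, the SAP does not settle how the early test is used. The TUG of someone who withdraws in week 7 could be coded as week 12, entered at its own date, or left out. Someone who leaves in week 4 is excluded under D5 but might be included under the SAP. The models also differ. Because neither document states precedence, the trial's only confirmatory test is not fixed in advance, and two careful analysts could obtain different answers.

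**Working it through.** **1. The plan's own figure.** Inputs from D6: difference 6.0 s, SD 6.0 s, 17 per group. D5 gives alpha 0.05; two-sided is assumed. The two-sample t test has 80.7% power at 17 per group and 78.1% at 16, so the stated 17 reproduces. Then 17/0.80 = 21.25, rounded up to 22 per arm, or 44. D6 also says: "The goal is to enroll 44 participants and graduate 17 participants per group (n=34) at the 12-week test point". That is (44 − 34)/2 = 5 lost per arm, or 22.7%, slightly above the stated 20%.

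**2. Formula.** Let f be the share of an arm's analysed participants whose value is carried forward, and d their mean change from the withdrawal test to week 12. The error in the CTL − EXP difference is

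−f(CTL) × d(CTL) + f(EXP) × d(EXP).

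The target is taken as the week-12 difference whatever happens after withdrawal. Neither document defines it.

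**3. Balanced withdrawal, linear divergence.** Assume CTL worsens by 6.0 s evenly over 12 weeks and EXP stays flat. Then d(CTL) = 6.0 × (1 − week/12), which is 3.0 s from week 6 and 1.5 s from week 9, and d(EXP) = 0. With 17 completers and k carried tests per arm, f = k/(17 + k).

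| k per arm | f | Shift, all at week 6 | Shift, all at week 9 |
|---|---|---|---|
| 1 | 1/18 = 0.056 | 0.17 s | 0.08 s |
| 2 | 2/19 = 0.105 | 0.32 s | 0.16 s |
| 3 | 3/20 = 0.150 | 0.45 s | 0.23 s |
| 5 | 5/22 = 0.227 | 0.68 s | 0.34 s |

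All shifts are toward no difference. Power with the reduced difference and 17 + k per arm stays between 81% and 86%.

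A middle case: if the 5 losses per arm are spread evenly over weeks 0 to 12, 2.5 fall after week 6. Then f = 2.5/19.5 = 0.128 and the shift is 0.128 × 1.5 = 0.19 s.

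**4. Other patterns.**
- Divergence complete by week 6: shift 0.
- All divergence after week 6, 20% carried per arm from week 6: 0.20 × 6.0 = 1.2 s. With 5 of 22 per arm: 1.36 s.
- Linear decline, all 10 losses in CTL at week 6: 10/22 × 3.0 = 1.36 s.
- Cancellation: 20% of each arm withdraw at week 6 and EXP withdrawers then decline at the CTL rate. The true difference is 6.0 − 0.2 × 3.0 = 5.4 s, and the rule also reports 5.4 s.
- Reversal: only EXP participants (20% of that arm) withdraw at week 6 and then decline at the CTL rate. The true difference is 5.4 s and the rule reports 6.0 s, which favours EXP.

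For scale, the standard error with 22 per arm is 6.0 × √(2/22) = 1.81 s, and D6 quotes a minimal detectable change of 3.4 s.

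**5. Precision if late withdrawers' week-12 values are treated as missing.** The unadjusted 95% half-width is t(0.975, 2n − 2) × 6.0 × √(2/n). On D6's counts, n = 19.5 gives 3.89 s and n = 17 gives 4.19 s.

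**6. Carry-forward against the SAP-type model.** Simulation with SD 6, correlation 0.6 between visits, linear CTL decline and all 24-week tests observed. With 22 per arm and 20% of each arm withdrawing at week 6, the true difference is 5.96 s, carry-forward gives 5.37 s and likelihood 5.96 s. Mean squared errors are 2.61 and 2.69. With 20 per arm and 12.5% carried from weeks 6 to 12, they are 2.47 and 2.76. Likelihood removes the bias but has slightly more total error.

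**The case against.** The best defence is that D5 is pre-specified and uses a fresh measurement, at most six weeks early, in a trial that calls itself a pilot. With no stated target, the rule can be read as defining the end-point for late withdrawers. It also has the slightly smaller mean squared error in both simulated cases and is exactly right in the cancellation case. All of this stands. It limits the point's seriousness, but does not resolve the clash with a 12-week end-point or with the SAP.

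A reader might infer several stronger things that the documents do not support:

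- **That no primary analysis is named.** D5 names one, with its covariates and a single test, and gives its mixed-effects model to the long-term outcomes. What is missing is a statement of which document governs.
- **That D5 contradicts itself by refusing to carry week 12 to week 24.** The cases are similar, not identical. The refusal concerns change after the intervention has ended; the early test falls within it.
- **That the rule biases the trial against EXP, or leaves it underpowered.** The direction depends on who withdraws and what happens to them afterwards. Power holds in the balanced cases computed.
- **That the shift has a firm ceiling of 0.6 or 0.7 s.** That holds only for roughly balanced withdrawal with linear divergence.

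**Conclusion.** The point holds as a minor one. The early-test rule and the missing order of precedence between D5 and the SAP are plain in the current text. The size of the effect is not, because the documents give neither the shape of the divergence, nor the split of losses around week 6, nor the balance between arms. They also do not say whether people with an early test count within the 20% loss.

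On balanced, linear assumptions the estimate moves by about 0.1 to 0.7 s toward no difference. Under late divergence or one-arm withdrawal it can move by about 1.2 to 1.4 s, and in other patterns the error cancels or changes sign. The main reason to act is that the single confirmatory test should have one definition, not that a large bias is expected.

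**What to change.** 1. State that the SAP's maximum-likelihood model governs the primary 12-week TUG comparison, and say whether D5's six-week exclusion applies to it.
2. Delete from D5 the clause that makes the early test the end-point. Treat an unmeasured week-12 TUG as missing. Record the early test at its actual date and do not code it as week 12.
3. Invite people who withdraw to the 12-week test as well as the 24-week one, and keep any values obtained.
4. Report the D5 carry-forward analysis as a sensitivity analysis.

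The cost is a wording change in D5, a short SAP amendment and the effort of the extra invitations. The half-width loss in step 5 of the working is at most 0.30 s (4.19 − 3.89), partly recovered from 24-week data, and mean squared error is slightly higher in some scenarios.

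Likelihood under missing at random does not capture a change of course after withdrawal. In the reversal case it gives about 6.0 s against a true 5.4 s if 24-week data add nothing. If a share m of withdrawers take the 12-week test, the estimate is 6 − 0.6m/(0.8 + 0.2m): 5.67 s at m = 0.5 and 5.40 s at m = 1. Item 3 is therefore needed alongside items 1 and 2. The documents give no rate at which withdrawers would return.

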 - b. Intrinsic Motivation Inventory (IMI) Interest and Enjoyment Subscales¹⁴
 - c. Participant compliance with exercise will be tracked as number of exercise sessions missed/possible sessions.
5. Healthcare Use:

- a. Number of healthcare provider visits scheduled and attended; from electronic medical record.
- b. Number of hospital contacts (emergency department visits and hospital admissions); from electronic medical record.

Interventions and Duration

Forty-four participants will be randomly assigned to two groups: 1) experimental (EXP) or 2) control (CTL). The entire intervention period is 12 weeks, with the primary end point at 12 weeks. At 24 weeks after initiation of intervention, each group will be asked to return for a follow-up test session.

Evaluations will take place using the following schedule:

Baseline, 12 and 24 weeks: Physical Performance Tests, Self-Report Physical Function Measures, Activity Measurement, Self-Efficacy questionnaire, Motivation questionnaire, Health Status questionnaire, and healthcare use assessment.

Baseline only: At Baseline testing, participants will also complete the following tests/measures/forms: 1) Folstein Mini-Mental State Examination,¹⁵ 2) Geriatric Depression Scale SF,^{16,17} 3) Chakrabarty scoring of residual-limb quality,¹⁸ 4) Residual limb length, 5) lower extremity sensory testing, 6) pre-amputation ambulatory status report, 7) type of prosthesis (socket, suspension, and foot), and 8) demographic information. Hemoglobin A1c measurements (for DM) and confirmation of PAD will be extracted from the participant medical records.

Continuously: Falls, Adverse Events (AEs), and Serious Adverse Events (SAEs) will be recorded and reported as needed.

Sample Size and Population

The target sample is 44 persons with recent transtibial amputation, resulting from PAD or DM complications.

Participants will be recruited from the University of Colorado Hospital and Denver Health.

Title: Collaborative-care rehabilitation to improve functional outcomes after dysvascular amputation

A. Abstract & Specific Aims

The primary objective of this project is to determine the efficacy of a collaborative-care, home-based exercise program for improving physical function, activity level, and health self-management within the first year following dysvascular transtibial amputation.

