Health self-management will be promoted in 3 primary ways: 1) action plan development with participant-directed goal setting, 2) participant self-tracking of activity (pedometers and exercise diary), and 3) participant education on problem-solving skills to manage chronic health conditions. Participants will also monitor their individual health condition (e.g., heart rate, time to claudication with walking, blood sugar, and blood pressure). These data will focus the weekly discussions (home or phone) over the 12-weeks.^{44,66,67}

Control (CTL) Group: CTL group participants will be contacted at the same interval (phone and home visits) as the EXP group (Figure 2) to ensure attention control between groups. Visits will

Table 3. EXP Group Rehabilitation Program

Category	Specific Components
Impairment-Based Exercise	
A. Strengthening* (3x/week)
 
Hip Extensors Hip Abductors Hip Adductors Knee Extensors Knee Flexors Ankle Plantar Flexors (intact limb) Trunk Stabilization
 
B. Stretching (3x/week)
 
Hip Flexors Knee Flexors

Activity-Based Intervention	• Walking Program (3x/week)
Health Self-Management	
 • Participant-tailored goals • Participant self-tracking of exercise and activity • Participant education on problem-solving skills for managing health

* List of options for strengthening program, priority muscles to be included in the program based on patient-researcher collaboration, with input from primary PT.

consist of recording problems reported by the participant. If health or rehabilitation questions arise that require professional advice during participant-researcher visits, the participant will be referred to his/her healthcare provider.

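### The six-week exposure rule in D5 drops hospital contacts of early withdrawers from a planned comparison between arms, and the SAP contains no such rule

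*Protocol*

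**What the plan says.** Hospital contacts are a listed outcome. The Protocol Synopsis, under Healthcare Use, has: "Number of hospital contacts (emergency department visits and hospital admissions); from electronic medical record". Hypothesis H4, under Exploratory Aim 1, expects fewer of them in the experimental arm at 12 and 24 weeks.

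Harms are handled separately. Under the continuous evaluations in the Synopsis: "Falls, Adverse Events (AEs), and Serious Adverse Events (SAEs) will be recorded and reported as needed". No cut-off at withdrawal is given. Falls, AEs and SAEs are not in the numbered outcome list.

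Section D5 sets the data rules:

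- On who is analysed: "data will only be analyzed for participants with sufficient intervention exposure, defined as six weeks".
- On early withdrawal: "Participants who withdraw before completing six weeks will be lost to follow-up and no imputation will be performed for missing data".
- On later withdrawal: "For participants who withdraw at or beyond six weeks of intervention, an early termination test will be performed and carried forward as the end-point".
- On the longitudinal model: "Also the mixed-effects model will not include data from subjects who drop prior to 6 weeks".
- The list of secondary outcomes ends with: "number of hospital encounters) using the same method as for the primary outcome".

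D5 also says that testing of every participant at 24 weeks will be attempted.

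The SAP is one paragraph. It applies a likelihood-based repeated measures model to every outcome, using whatever data are available under a missing-at-random assumption. It states no exclusion by exposure. Neither document defines a safety analysis set, a summary of harms by arm, or event follow-up after withdrawal.

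**The concern.** A rule based on exposure is most troublesome for an outcome that can itself end exposure. A participant admitted in week 3 may leave the study because of that admission. D5 then removes both the person and the admission from the comparison of hospital encounters. The data need not be lost, because the source is the medical record and no visit is required.

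The arms may not be affected equally. Under D4 the experimental arm does progressive strengthening and walking at home without supervision, while control visits only record reported problems. If admissions led to early withdrawal more often in the experimental arm, the exclusion would move the result towards H4. If this happened more often in the control arm, it would move the result the other way.

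The word used in D5 is simply data, without restriction to efficacy. It is therefore unclear whether falls, AEs and SAEs in early withdrawers would count in a table by arm.

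**Working it through.** **Step 1. How many people could be affected.** Section D6 aims to enrol 44 and have 34 complete week 12, with 20% loss.

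- The plan's own figure: 34 / (1 − 0.20) = 42.5, rounded up to 43, against 44 planned. It reproduces to within one person.
- Non-completers implied by the goal: 44 − 34 = 10, and 10/44 = 22.7%.
- D6 does not say how many of these leave before week six. If none do, D5 excludes 0 people; if all do, it excludes 10. The range is 0 to 10 of 44.

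**Step 2. Follow one case through both documents.** Take a participant admitted in week 3 who then withdraws.

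| Item | D5 as written | SAP as written |
|---|---|---|
| The admission, as a hospital contact | Excluded: the exposure rule applies and the outcome uses the primary method | Not excluded |
| The admission, as an SAE | Recorded and reported under the Synopsis; left out of any summary by arm if D5 is read literally | No summary planned |
| Hospital contacts after withdrawal | Participant treated as lost to follow-up | Usable if collected, but the SAP cannot supply what was not collected |

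The first row is a direct consequence of the text and also shows the conflict between the documents. The second depends on how broadly D5 is read.

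**Step 3. Illustration of direction only.** The counts here are assumptions, not figures from the documents. Assume 22 per arm (44/2), with at least one hospital contact in 6 experimental and 3 control participants. Let x of the 6 withdraw before week six and be excluded:

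difference(x) = (6 − x)/(22 − x) − 3/22

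| x | Experimental | Control | Difference (points) |
|---|---|---|---|
| 0 | 6/22 = 27.3% | 13.6% | 13.6 |
| 1 | 5/21 = 23.8% | 13.6% | 10.2 |
| 2 | 4/20 = 20.0% | 13.6% | 6.4 |
| 3 | 3/19 = 15.8% | 13.6% | 2.2 |
| 4 | 2/18 = 11.1% | 13.6% | −2.5 |

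If instead one affected control participant is excluded, the difference is 6/22 − 2/21, about 18 points, so the error goes the other way. If those excluded in each arm have the same share of contacts as those who stay, the proportions do not change. The result therefore depends on who withdraws early and why, which the documents cannot tell us. D5 would model the number of encounters; the proportion with any contact is used here for simplicity.

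**The case against.** The best defence is that D5 is plainly an efficacy rule. The exposure sentence follows the TUG analysis, and the sentences after it concern early termination tests, imputation and 24-week testing, none of which fits an adverse event. Harms have their own line in the Synopsis with no withdrawal cut-off. For falls, AEs and SAEs this largely stands: the literal reading is possible but not the only one. For hospital encounters it fails, because D5 itself places them under the primary method.

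A second defence is that the SAP already uses all observations, and that D5 means to test everyone at 24 weeks. Neither settles the matter. The SAP and the Protocol appear to carry the same date, and the SAP does not say that it overrides D5. A participant who returns at 24 weeks after leaving before week six is still excluded from the longitudinal model under D5.

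A reader might go further and infer that early harms vanish from a safety comparison, so that the programme would be reported as safer than it was. The documents do not support that. No comparison of falls, AEs or SAEs by arm is planned, and these events would still be recorded and reported.

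A reader might also infer that falls in weeks 12 to 24 would rest on long recall, since D4 says of the self-monitoring data: "These data will focus the weekly discussions (home or phone) over the 12-weeks". But D4 refers to Figure 2 for the contact interval, and that figure is not available in the text reviewed. Silence in the remaining text is not a contradiction of continuous recording.

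Finally, the medical record will not show falls or AEs that involve no hospital contact, so continued extraction recovers only part of the information.

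**Conclusion.** The point holds for hospital contacts. Followed as written, D5 removes emergency visits and admissions that lead to withdrawal before week six from a planned between-arm comparison, although their source remains accessible. The SAP contains no such exclusion, so two analysts could produce different results from the same trial.

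For falls, AEs and SAEs the finding is narrower: there is no defined summary by arm and no analysis set for one, and D5's unrestricted wording leaves early withdrawers' events in doubt.

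At most 10 of 44 participants are affected, and possibly none. The size and direction of any bias cannot be taken from the documents; the table in step 3 rests on assumed counts. The change is worth making because the defect is clear in the text and cheap to remove.

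**What to change.** In D5 and the SAP:

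1. Limit the six-week rule to the efficacy outcomes measured at test sessions, or remove it so that D5 matches the SAP. Either choice also frees the provider-visit count, which has the same medical-record source.
2. State that hospital contacts are compared, and falls, AEs and SAEs summarised, by arm for all randomised participants, with person-time.
3. Replace the lost-to-follow-up clause with wording to this effect: *participants who stop the intervention before six weeks remain in the study for medical-record extraction and event recording to week 24, where they consent.*

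The cost is the wording, consent that covers continued extraction, and record extraction for at most about 10 more people. Reported event rates may look less favourable. The sample size does not change, and no extra participant calls are proposed, since they would add contact in the period used to judge whether effects persist.

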 - (1) H3: The rehabilitation program group will tend to have greater positive change in ratings on the Self-Efficacy in Managing Chronic Disease (SEMCD) questionnaire and Intrinsic Motivation Inventory (IMI) Interest and Enjoyment Subscales, compared to the standard of care group at 12 and 24 weeks following initiation of intervention.
 - (2) H4: The rehabilitation program group will tend to have higher numbers of attended healthcare provider appointments and lower numbers of hospital contacts at 12 weeks and 24 weeks, compared to the standard of care group.

2. Exploratory Aim 2 (EA2) and Hypothesis (H4) are:

- a) EA2: Identify factors predictive of physical activity level and disability measured by activity monitors and self-reported disability (World Health Organization Disability Assessment Schedule 2.0), respectively.
- b) H5: Significant predictors of physical activity and disability will be identified from the categories of demographic/anthropometric, activity/mobility, health behaviors, physical health, amputated-limb health, contralateral-limb health, cognitive/affective health, and healthcare use factors for participants at 24 weeks following intervention, regardless of group assignment.

B. Background and Significance

B1. Significance. Limitations in physical function are common following dysvascular major lower limb amputation.^{28,29,31} This is a significant issue considering that dysvascular amputation is becoming increasingly more common in the United States. Dysvascular amputation is operationally defined as amputation resulting from severe PAD with critical limb ischemia or severe DM with dense distal sensory and motor neuropathy leading to a non-healing wound (or a combination of these two related, but separate pathophysiologies). The projection of 2.3 million people living with amputation in the United States by the year 2050 represents an increase of nearly 100% from current values.¹⁹ As a result, dysvascular amputation has become a major healthcare issue in the U.S, including an economic problem.³²

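### Record-based healthcare-use counts inherit the TUG rules: an unnecessary six-week exclusion and, on a natural reading, part-period counts analysed as 12-week counts with no exposure term

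*Protocol*

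**What the plan says.** Protocol D5 (Data Analysis) names the two healthcare-use counts among the secondary 12-week analyses: "number of healthcare provider visits, and number of hospital encounters) using the same method as for the primary outcome". The primary method has three parts.

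- **Early withdrawals.** "Participants who withdraw before completing six weeks will be lost to follow-up and no imputation will be performed for missing data". D5 restricts analysis to participants with at least six weeks of intervention.
- **Later withdrawals.** "For participants who withdraw at or beyond six weeks of intervention, an early termination test will be performed and carried forward as the end-point".
- **Model.** A linear model for TUG, with "explanatory variables being primary medical diagnosis (PAD, DM, or both), rehabilitation site, treatment group, and baseline TUG". Follow-up time is not a term, and no offset or rate is mentioned.

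The Synopsis (Healthcare Use) gives the source of both counts: "Number of healthcare provider visits scheduled and attended; from electronic medical record" and "Number of hospital contacts (emergency department visits and hospital admissions); from electronic medical record". Its evaluation schedule places a healthcare use assessment at baseline, 12 and 24 weeks, alongside the performance tests. Neither document defines the window over which events are counted, or when counting ends for someone who withdraws.

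H4, under Exploratory Aim 1, predicts that EXP will show "higher numbers of attended healthcare provider appointments and lower numbers of hospital contacts" at both 12 and 24 weeks.

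The SAP carries the same version date as the protocol. It analyses every outcome by maximum likelihood in a repeated measures model, using whatever data are available and assuming they are missing at random. It adjusts for baseline value, site (VA or not), DM and PAD. It mentions neither carry-forward nor the six-week exclusion, and it too has no exposure term. Neither document says which prevails.

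**The concern.** A TUG time measured at week 7 is still a TUG time. A cumulative count closed at week 7 covers 7/12 of the period it is meant to describe. A rule that is merely debatable for a performance test therefore changes the meaning of a count.

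Two things are at stake. First, the exclusion before week 6 removes randomised participants whose outcome could be read from the record without their attendance. Second, if counts end at the early termination session, the arm means are too low, and unequal withdrawal distorts the comparison. More or earlier withdrawal in EXP would look like fewer hospital contacts, as H4 predicts, and would also hide attended visits, against H4. The protocol intends to use trends under this aim for a power calculation for a future study, so an error could carry into that design.

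**Working it through.** **Plan's own figures.** Neither document gives a rate, a variance or a sample size for the counts. The TUG sample size does reproduce: a difference of 6.0 s and SD of 6.0 s at two-sided 0.05 (sidedness assumed) give 80.7% power by t-test at 17 per group. It says nothing about the counts.

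**Inputs from the documents.** Count period 12 weeks; carry-forward from week 6 (D5); 20% loss at 12 weeks, not split by arm or by week (D6); 44 enrolled.

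**Assumptions.** Constant event rate; counts end at withdrawal; no true treatment effect; withdrawal shares by arm as shown below.

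**Step 1: the exclusion.** If all of the planned 20% loss fell before week 6, about 44 × 0.20 = 8.8, or 9 participants, would be dropped from an outcome still obtainable from the record. If none did, the exclusion would cost nothing.

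**Step 2: understatement in one arm.** Let p be the share of an arm's analysed participants who withdraw at or after week 6, and w the withdrawal week. The share of the true 12-week mean retained is f = 1 - p(1 - w/12).

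With p = 0.20, taking the planned loss as wholly from week 6 onward:

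- w = 6: f = 1 - 0.20 × 0.50 = 0.90, a loss of 10%
- w = 9: f = 1 - 0.20 × 0.25 = 0.95, a loss of 5%
- w = 11: f = 1 - 0.20 × 0.083 = 0.983, a loss of 1.7%

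If both arms have the same p and w, the ratio of means stays at 1.00. Any true difference in means, which is what the linear model estimates, shrinks by the same percentage.

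**Step 3: between-arm ratio, f(EXP)/f(CTL), when the true ratio is 1.00.**

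| Assumed withdrawal, EXP / CTL | Week 6 | Week 9 | Week 11 |
|---|---|---|---|
| 20% / 20% | 1.00 | 1.00 | 1.00 |
| 30% / 10% | 0.85/0.95 = 0.895 | 0.925/0.975 = 0.949 | 0.975/0.992 = 0.983 |
| 40% / 0% | 0.80 | 0.90 | 0.967 |
| 10% / 30% | 1.118 | 1.054 | 1.017 |

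For the 30%/10% row, the linear model would show a spurious difference of 0.10, 0.05 or 0.017 times the true 12-week mean.

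**Step 4: timing matters as well as number.** An arm with 20% leaving at week 6 loses 0.20 × 0.50 = 10%. An arm with 30% leaving at week 11 loses 0.30 × 0.083 = 2.5%. The arm with more withdrawals need not be the more understated one.

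**Step 5: size against precision.** With 17 per arm and assumed mean counts of 1 to 6 and dispersion k of 0.5 to 1, the standard error of the log rate ratio is about √[(2/17)(1/mean + k)]. That is 0.28 (mean 6, k = 0.5) to 0.49 (mean 1, k = 1). The 30%/10% case gives ln 0.949 = -0.053 at week 9, or 0.11 to 0.19 standard errors, and ln 0.895 = -0.111 at week 6, or 0.23 to 0.40.

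**Step 6: after correction.** With records read to week 12 for everyone, or with an offset for time observed under a constant rate, the ratio is 1.00 in every cell.

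**The case against.** The strongest reply is that truncation is not in the text. What D5 carries forward is a test, and the counts are not tests: they come from the medical record, which staff could read to week 12 whether or not the participant attends. D7, which describes the test sessions, does not list healthcare use among the measures. This stands. A reader might infer that the plan stops the count at withdrawal; the documents do not say so. Against it, the Synopsis schedules the healthcare use assessment beside the tests, and nothing directs staff to extract records beyond withdrawal. The reading is natural but not established. The six-week exclusion, by contrast, is explicit.

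A second reply is that the SAP supersedes the problem, since it covers all outcomes without carry-forward. This stands only in part. The SAP does not say whether a count taken at early termination is available 12-week data. If it is, the same understatement enters; if it is not, obtainable data are treated as missing. With matching dates and no order of precedence, the two documents conflict.

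Third, a reader might infer a bias in favour of EXP, or one that always falls hardest on the arm with more withdrawals. Neither follows. The documents give no withdrawal by arm or week, CTL has the same contact schedule as EXP, the direction reverses if CTL loses more, and Step 4 shows that timing can outweigh number.

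Finally, the stakes are modest. Although D5 calls these analyses secondary, H4 sits under an exploratory aim that the protocol expects to lack power, and the plausible bias is a fraction of a standard error. This stands and limits the severity.

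**Conclusion.** The point holds in a limited form and is minor to moderate. D5 applies to two cumulative, record-based counts a method designed for a timed test. One consequence is explicit: participants who leave before six weeks are excluded from outcomes that do not need their attendance. The other is conditional: if the count is taken at early termination, a part-period count stands in for a 12-week count and no model term corrects it. An arm mean is then understated by at most 10% with 20% withdrawing, all at week 6, and by less if they leave later. The between-arm ratio is distorted only if withdrawal or its timing differs by arm, and the 0.895 to 0.983 range for 30% against 10% rests on assumed shares and a constant rate. The documents do not support the claim that truncation is prescribed or that it favours EXP. The TUG analysis is unaffected.

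**What to change.** 1. In D5, exempt the healthcare-use counts from the six-week exclusion and from carry-forward.
2. Define the counts over fixed windows of 0-12 and 0-24 weeks, and extract the record over both for every randomised participant unless record access is withdrawn.
3. Where follow-up is still incomplete (death, access withdrawn), use a count model, such as negative binomial or quasi-Poisson, with log follow-up time as offset. Report rate ratios with 95% confidence intervals. With full extraction the offset is nearly constant and matters only for these few participants.
4. Reconcile D5 with the SAP on carry-forward, and state the counts' analysis population and model in both.

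The cost is wording and slightly longer record extraction. No gain in power should be expected; the benefit is a count with a defined meaning. The offset assumes a constant rate and uninformative withdrawal, so it would not repair a case where hospitalisation itself leads to withdrawal. Full extraction is therefore the main remedy and the offset the fallback.
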